1.2 Schedule of Events

Table 1: Schedule of Events

Visit Number		1	2	3	4	5	6	7	8	9	USV
Type of Visit/Contact	C	C	C	SC	SC	C	SC	SC/C	SC	SC/C	C
Month Timepoint						M1	M3	M6	M9	M12	Up to M12
Study Visit	Screening ¹	D1 (Baseline)	D4	D8	D15	D29	D91	D181	D271	D361/EoS	USV
Window Allowance (Days)	-28	N/A	-2	±3	±3	-7 to +3	±5	±14	±14	±14	N/A
Informed consent form, demographics, concomitant medications, medical history ²	X										
Inclusion/exclusion criteria	X	X									
Physical examination ³	X										
Vital signs ⁴	X	X									
Pregnancy testing ⁵	X	X									
Randomization		X									
Study vaccination (including 30-minute post-dosing observation period) ⁶		X									
Collection of Edmonton Frail Scale ⁷		X									
Blood collection for humoral immunogenicity		X ⁸				X		X ⁹		X ⁹	
Genomic sample (optional)		X ⁸									
Transcriptomic sample (optional)		X ⁸				X					
Optional blood sample for potential biomarker analysis ¹⁰			X								
NP swab for virus detection ¹¹											X
eDiary activation for recording solicited ARs (7 days) ¹²		X									
Review of eDiary for solicited ARs				X							
Symptom Reporting eDiary activation ¹³		X									
Symptom Reporting eDiary for collection of symptoms of ILI ¹⁴		Once weekly									

Visit Number		1	2	3	4	5	6	7	8	9	USV
Type of Visit/Contact	C	C	C	SC	SC	C	SC	SC/C	SC	SC/C	C
Month Timepoint						M1	M3	M6	M9	M12	Up to M12
Study Visit	Screening ¹	D1 (Baseline)	D4	D8	D15	D29	D91	D181	D271	D361/EoS	USV
Window Allowance (Days)	-28	N/A	-2	±3	±3	-7 to +3	±5	±14	±14	±14	N/A
Review of Symptom Reporting eDiary ¹⁵		Review participant-recorded ILI starting on Day 1 through Day 361 (Month 12)/EoS									
Follow-up safety call				X	X		X	X ¹⁶	X	X ¹⁶	
eDiary collection of EQ-5D-5L ¹⁷		X	eDiary prompts ¹⁸								
eDiary collection of WPAI:ILI ¹⁹			eDiary prompts ²⁰								
Recording of unsolicited AEs		X		X	X	X					
Recording of SAEs, AESIs, and MAAEs, as well as AEs that led to discontinuation and relevant concomitant medications/procedures ²¹		X		X	X	X	X	X	X	X	X
Recording of concomitant medications and non-study vaccinations ²²		X		X	X	X					
Recording of hospitalizations and outpatient treatment-related to or for the treatment of the MAAE or SAE ²³		X		X	X	X	X	X	X	X	X
Study completion										X	

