18. All participants will receive eDiary prompts to complete the EQ-5D-5L at Day 1 (baseline), Day 91, Day 181, Day 271, and Day 361 (Month 12)/EoS. For participants reporting symptoms of ILI, the EQ-5D-5L responses will be collected using the eDiary on the day of the symptoms reporting (+1 day) and 5 days (+1 day) later.
19. WPAI consists of 6 questions, which can quantitatively assess the amount of absenteeism, presenteeism, overall work impairment, and activity impairment attributable to a patient's health issues based on a 1-week recall period. The WPAI is available in different versions, such as WPAI: Specific Health Problem (WPAI:SHP), which can be adapted to a specific disease.
20. For participants reporting symptoms of ILI, the WPAI over the previous 7 days will be collected using the eDiary 5 days (+1 day) following the start of ILI symptoms reporting.
21. Trained study personnel will call all participants to collect information relating to any MAAEs, AEs leading to study discontinuation, SAEs, AESIs, information on concomitant medications associated with those events, and any non-study vaccinations. All concomitant medications relevant to or for the treatment of an SAE, AESI, or MAAE will be recorded from Day 1 through Day 361 (Month 12)/EoS.
22. All concomitant medications and non-study vaccinations will be recorded through 28 days after IP injection (including receipt of any authorized or investigational COVID-19 vaccine).
23. All hospitalizations, outpatient/physician visits, emergency room/urgent care visits, and telemedicine visits associated with MAAEs or SAEs will be recorded from Day 1 through Day 361 (Month 12)/EoS.

TABLE OF CONTENTS

CLINICAL STUDY PROTOCOL	1
PROTOCOL APPROVAL – SPONSOR SIGNATORY	2
DECLARATION OF INVESTIGATOR.....	3
PROTOCOL AMENDMENT SUMMARY OF CHANGES TABLE.....	4
1. PROTOCOL SUMMARY.....	11
1.1 Protocol Synopsis	11
1.2 Schedule of Events	27
TABLE OF CONTENTS.....	31
LIST OF TABLES	36
LIST OF FIGURES	36
LIST OF ABBREVIATIONS.....	37
2. INTRODUCTION	40
2.1 Study Rationale.....	40
2.2 Background and Overview	40
2.2.1 mRNA-1010	40
2.2.2 Nonclinical Studies.....	41
2.2.3 Clinical Studies.....	42
2.3 Benefit/Risk Assessment	43
2.3.1 Known Potential Benefits	43
2.3.2 Risks From Study Participation and Their Mitigation.....	43
2.3.3 Overall Benefit/Risk Conclusion.....	44
3. OBJECTIVES AND ENDPOINTS	45
4. STUDY DESIGN	48
4.1 General Design	48
4.2 Scientific Rationale for Study Design	50

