3. OBJECTIVES AND ENDPOINTS

The objectives which will be evaluated in this study and endpoints associated with each objective are provided in [Table 2](#).

Table 2: Study Objectives and Endpoints

Objectives	Endpoints
Primary	

 To evaluate the humoral immunogenicity of mRNA-1010 relative to that of an active comparator against vaccine-matched influenza A and B strains at Day 29 	
 GMT at Day 29 as measured by HAI assay Proportion of participants reaching seroconversion at Day 29 as measured by HAI assay

 To evaluate the safety and reactogenicity of mRNA-1010 	
 Frequency and grade of each solicited local and systemic reactogenicity AR during a 7-day follow-up period post vaccination Frequency and severity of any unsolicited AEs during the 28-day follow-up period post vaccination Frequency of any SAEs, AESIs, MAAEs, and AEs leading to discontinuation from Day 1 through Day 361 (Month 12)/EoS
Secondary	

 To further evaluate the immunological response of mRNA-1010 (for superiority) relative to an active comparator against vaccine-matched influenza A virus strains at Day 29 	
 GMT at Day 29 as measured by HAI assay Proportion of participants reaching seroconversion at Day 29 as measured by HAI assay

 To evaluate relative vaccine efficacy to prevent influenza caused by any strain of influenza virus 	
 First episode of RT-PCR–confirmed protocol-defined ILI that begins at least 14 days postvaccination through Day 181 (Month 6)/end of influenza season caused by any strain of influenza virus regardless of antigenic match to the strains selected for the seasonal vaccine First episode of RT-PCR–confirmed Centers for Disease Control and Prevention (CDC)–defined ILI that begins at least 14 days postvaccination through Day 181 (Month 6)/end of influenza season caused by any strain of influenza virus regardless of

Objectives	Endpoints

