8.9 Safety Assessments

Safety assessments will include monitoring and recording of the following for each participant, according to the SoE ([Table 1](#)):

- Solicited local and systemic ARs ([Section 8.11.3](#)) that occur during the 7 days following the study injection (ie, the day of injection and 6 subsequent days). Solicited ARs will be recorded daily using eDiaries ([Section 8.9.4](#)).

- Unsolicited AEs observed or reported during the 28 days following the study injection (ie, the day of injection and 27 subsequent days). Unsolicited AEs are defined in [Section 8.11.1](#).
- AEs leading to discontinuation from study participation from Day 1 through Day 361 (Month 12)/EoS or withdrawal from the study.
- MAAEs from Day 1 through Day 361 (Month 12)/EoS or withdrawal from the study. Medically attended AEs are defined in [Section 8.11.4](#).
- SAEs ([Section 8.11.2](#)) and AESIs ([Section 8.11.6](#)) from Day 1 through Day 361 (Month 12)/EoS or withdrawal from the study.
- Details of all pregnancies in female participants will be collected after the start of study vaccine and until the end of their participation in the study ([Section 8.11.7](#)). All pregnancies must be followed to determine the outcome.

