8.9.3 Safety Telephone Calls

A safety telephone call is a telephone call made to the participant by trained site personnel. This call will follow a script, which will facilitate the collection of relevant safety information. Safety telephone calls will follow a schedule for each participant, as shown in the SoE (Table 1). The participant will be interviewed according to the script about occurrence of AEs, MAAEs, SAEs, AESIs, AEs leading to withdrawal from study participation, concomitant medications associated with those events, and any non-study vaccinations (Section 8.11.14). All safety information collected from the telephone contact must be documented in source documents as described by the participant and not documented on the script used for the safety telephone contact. An unscheduled follow-up safety call may be triggered if an eDiary record results in identification of a relevant safety event.

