8.11.8 Recording and Follow-up of an AE and/or SAE

The investigator is responsible for ensuring that all AEs and SAEs are recorded in the eCRF and reported to the Sponsor.

Solicited ARs will be collected from Day 1 through 7 days after the vaccine dose (ie, the day of injection and 6 subsequent days). Other (unsolicited) AEs will be collected from Day 1 through 28 days after the vaccine dose (ie, the day of injection and 27 subsequent days).

Medically attended AEs, SAEs, and AESIs will be collected from participants as specified in the SoE ([Table 1](#)) from Day 1 until the end of their participation in the study.

At every clinic visit or telephone contact, participants will be asked a standard question to elicit any medically related changes in their well-being (including surveillance for respiratory viral infection symptoms) according to the scripts provided. Participants will also be asked if they have been hospitalized, had any accidents, used any new medications, changed concomitant medication regimens (both prescription and over-the-counter medications), or had any non-study vaccinations.

In addition to participant observations, physical examination findings and other documents relevant to participant safety classified as an AE will be documented on the AE page of the eCRF.

After the initial AE/SAE report, the investigator is required to proactively follow each participant at subsequent visits/contacts. All AEs and SAEs will be treated as medically appropriate and followed until resolution, stabilization, the event is otherwise explained, or the participant is LTFU (as defined in [Section 7.2](#)).

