- In the derivation of max/min on-treatment values and max/min change from baseline values for safety analyses
- In individual participant data listings as appropriate

Visit windowing rules: The analysis visit windows for protocol-defined visits are provided in [Section 9.3](#).

Analysis Periods:

The following analysis periods will be used for safety analyses in the study:

- 7 days post-vaccination: this period includes the day of vaccination and 6 subsequent days. This analysis period will be used for solicited local/systemic ARs and SAEs that occur during this time.
- Up to 28 days post-vaccination: this period starts from the day of vaccination and spans 28 days to include the day of vaccination and 27 subsequent days. This analysis period will be used for unsolicited AE, except for solicited AR, unless specified otherwise.
- Up to 180 days post-vaccination: this period starts from the day of vaccination and spans to 180 days to include the day of vaccination and 179 subsequent days. This analysis period will be used for MAAEs, SAEs, and AESIs
- Up to data cutoff date: this period starts from day of vaccination and continues through the data cut-off date applied at planned analyses as specified in [Section 6.8](#).
- Overall study period: this period starts on Day 1 and continues through the earliest of the following: study completion, discontinuation from the study, or death.

For the Day 29 primary analysis, the analysis will include all participants' immunogenicity data and safety data collected up to Day 29 post-vaccination. For the 6-months analysis, the analysis may include a subset of participants' immunogenicity data (the first 1000 randomized participants per study design) collected up to Day 181, vaccine efficacy data on Day 181/end of influenza season, and safety data up to 180 days post-vaccination. Additional details are presented in [Section 6.8](#).

Incomplete/missing data:

- Imputation rules for missing prior/concomitant medications, non-study vaccinations and procedures are provided in [Section 9.4](#).
- Imputation rules for missing AE dates are provided in [Section 9.4](#).
- For summarizations of GMTs, antibody titers reported as below the lower limit of quantification (LLOQ) will be replaced by 0.5 x LLOQ. Values that are greater than the upper limit of quantification (ULOQ) will be converted to the ULOQ.
- Other incomplete/missing data will not be imputed, unless otherwise specified.

Subgroups:

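### The Day 29 visit, the last contact marked for recording unsolicited AEs, may be held as early as Day 22, so scheduled ascertainment can stop up to 6 days short of the 28-day safety endpoint

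*Protocol*

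**What the plan says.** Protocol Section 3 (Table 2) lists as a primary safety endpoint "Frequency and severity of any unsolicited AEs during the 28-day follow-up period post vaccination". Protocol 8.9 fixes the period as "Unsolicited AEs observed or reported during the 28 days following the study injection (ie, the day of injection and 27 subsequent days", to be recorded according to the Schedule of Events. Protocol 8.11.8 agrees: "Other (unsolicited) AEs will be collected from Day 1 through 28 days after the vaccine dose". SAP 6.1 uses the same analysis period: "this period starts from the day of vaccination and spans 28 days to include the day of vaccination and 27 subsequent days". All four therefore describe Day 1 to Day 28.

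In Protocol Table 1 the row "Recording of unsolicited AEs" is marked at D1, D8, D15 and D29 and is blank at every later visit and at unscheduled visits. SAP Table 6 repeats it. The D29 column has a window of -7 to +3 days. The row for concomitant medications and non-study vaccinations ends at the same visit, although footnote 22 asks for these through 28 days after injection.

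The next scheduled contact is the D91 safety call (±5 days). Footnote 21 describes the calls this way: "Trained study personnel will call all participants to collect information relating to any MAAEs, AEs leading to study discontinuation, SAEs, AESIs", together with related medications and non-study vaccinations. Protocol 8.9.3 is wider: "The participant will be interviewed according to the script about occurrence of AEs, MAAEs, SAEs, AESIs".

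**The concern.** The endpoint is defined in days since injection, but the last scheduled opportunity to ask about it is tied to a visit that may legitimately take place before those days have passed. A site can follow the plan exactly and still not ask some participants about the final part of the period.

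The planned tables would not show this. Under SAP 6.1 percentages are taken over all participants in the group within the analysis set, and SAP 6.6.2 presents unsolicited TEAEs as up to 28 days for everyone. The exposure table in SAP 6.2.6 counts participants with at least 28 days of study duration after injection. Someone seen on Day 22 who stays in the study counts as complete there. Absolute frequency is itself the endpoint, and incomplete ascertainment can only lower it.

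**Working it through.** **The plan's own safety figure.** Protocol 9.3 and SAP 4.3 give about a 95% probability of seeing at least one participant with an AE, with 3000 exposed and a true rate of 0.1%. Check: 1 − (1 − 0.001)^3000 = 0.9503. The figure reproduces; it assumes complete observation.

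**Visit window.** Earliest D29 visit: 29 − 7 = Day 22. Latest: 29 + 3 = Day 32.

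**Full days of the Day 1–28 period left after a visit on day v:** max(0, 28 − v).

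| D29 visit held on | Days left | Share of 28 days |
|---|---|---|
| Day 22 | 6 | 21.4% |
| Day 23 | 5 | 17.9% |
| Day 24 | 4 | 14.3% |
| Day 25 | 3 | 10.7% |
| Day 26 | 2 | 7.1% |
| Day 27 | 1 | 3.6% |
| Days 28 to 32 | 0 | 0% |

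**Average over participants.** The documents do not give the distribution of visit days. Assuming an even spread over the 11 days from Day 22 to Day 32: (6 + 5 + 4 + 3 + 2 + 1)/11 = 21/11 = 1.9 days, and 1.91/28 = 6.8%. This is observation time, not a share of AEs.

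**Delay to the next scheduled contact.** D91 ± 5 is Day 86 to Day 96. From a Day 22 visit that is 86 − 22 = 64 to 96 − 22 = 74 days.

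**Sensitivity of the 95% figure.** Suppose a fraction f of participants attends on Day 22 and the rest on Day 28 or later, with a constant AE hazard over 28 days and no later capture. The last assumption is deliberately pessimistic. Covered person-time is c = 1 − f × 6/28, and the detection probability is 1 − (1 − 0.001c)^3000.

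| f | Covered person-time | Detection probability |
|---|---|---|
| 10% | 97.9% | 94.7% |
| 25% | 94.6% | 94.2% |
| 50% | 89.3% | 93.1% |
| 100% | 78.6% | 90.5% |

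**What remains covered after an early visit.** SAEs, AESIs, MAAEs and AEs leading to discontinuation are collected to Day 361 (Protocol 8.9). ILI symptoms are prompted weekly, and Protocol 8.11.5 requires any illness assessed for protocol-defined ILI or suspected SARS-CoV-2 through Day 28 to be captured as an AE. Footnote 21 keeps non-study vaccinations in the calls. That leaves mainly AEs that are non-serious, not medically attended and not ILI, and routine concomitant medications.

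**The case against.** The best counter-argument is that the protocol does not close the door at the D29 visit. The call script in 8.9.3 names general AEs separately from MAAEs and SAEs. Protocol 8.11.8 adds: "At every clinic visit or telephone contact, participants will be asked a standard question to elicit any medically related changes". Protocol 8.11.11 sends every unsolicited AE reported or observed during the study to the AE page, and 8.11.14 says the diaries have free-text space for unsolicited AEs. An event that starts on Day 25 and is mentioned at D91 is therefore recordable and falls inside the SAP's period. A reader might infer that early attenders have no later contact at which such an event could be recorded. The documents do not support that: what is missing is a later contact marked for it in Table 1.

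What this does not supply is dependable capture. The next scheduled use of the script or the general question is about two months or more after an early visit and relies on memory. It may also come after the Day 29 lock, because Protocol 9.6.1 and SAP 6.8 trigger the primary analysis on completion of the Day 29 visit; an event reported later could still enter the final analysis. Footnote 21 and the Table 1 row do not list unsolicited AEs at D91, so the schedule and 8.9.3 disagree. The free-text space in 8.11.14 is described with the diary for solicited reactions, which Table 1 schedules for 7 days; the section does not say when that space closes. The diary that continues is scheduled for ILI symptoms.

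It is also fair to say that the unsolicited AE summaries are descriptive and that both arms share the same window under observer-blinding. Both points limit the consequence; neither restores the missing days.

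**Conclusion.** The point holds as a gap in scheduled ascertainment. A participant seen on Days 22 to 27 has 1 to 6 of the 28 days after the last marked contact, up to 21% for that individual. The average of 1.9 days (6.8% of observation time) rests on an assumed even spread of visits, and the true share of early attenders is unknown. The expected effect is a modest understatement of 28-day unsolicited AE frequency, and of routine concomitant medication use, in both arms.

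Two stronger inferences should be resisted. First, a trial-wide loss near 21% of AEs would need almost everyone to be seen on Day 22, a constant hazard and no later reporting. The documents give no attendance data, and 8.9.3, 8.11.8 and 8.11.11 contradict the assumption of no later reporting. Second, the documents show no differential bias between arms. The point does not touch the follow-up of SAEs, AESIs or MAAEs. It is worth correcting because the endpoint is primary, the shortfall would not be visible in the planned tables, and the remedy is cheap.

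**What to change.** 1. Keep the D29 visit window. For any participant whose D29 visit is before Day 28, add one electronic prompt or short call on or after Day 29 that records unsolicited AEs and concomitant medications through Day 28. Mark it in Protocol Table 1 and SAP Table 6.
2. Reconcile footnote 21 with Protocol 8.9.3, so that it is clear whether the safety calls collect general AEs with onset through Day 28.
3. In SAP 6.6.2, report by vaccination group the number of participants with unsolicited AE ascertainment through Day 28.

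The cost is a small schedule amendment and one brief extra contact for early attenders, with no additional visit or sample. If the contact cannot be added, item 3 alone still lets readers judge how complete the 28-day endpoint is.

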8.9.1 Pregnancy Screen and Testing

A pregnancy test via blood or point-of-care urine test will be performed for all female participants of childbearing potential at the Screening Visit and before the vaccine dose on Day 1, if Day 1 is not on the same day as the Screening Visit. At the discretion of the investigator, a pregnancy test either via blood or point-of-care urine can be performed at any time. Additional pregnancy testing during the study may also be performed if required by local regulatory requirements. The participant's FSH level may be measured at the Screening Visit, as necessary, and at the discretion of the investigator, to confirm postmenopausal status ([Section 11.2](#)).

Further details on reporting and follow-up of pregnancy are provided in [Section 8.11.7](#).

8.9.2 Assessments for Respiratory Viral Infections

The NP swab specimen(s) for pathogens, including influenza virus and SARS-CoV-2, will be collected any time from Day 1 to Day 361 (Month 12)/EoS if participants have protocol-defined ILI or symptoms suggestive of COVID-19 or other upper or lower respiratory infection, as defined in the ILI Case Definitions ([Section 8.11.5](#)). If participants experience these signs or symptoms, they will be instructed to contact the clinic to have an NP swab collected for testing. Nasopharyngeal swabs may be collected as part of a home visit in lieu of a clinic visit. In the event that NP swabs during ILI cannot be collected, any available influenza and/or SARS-CoV-2 testing results performed outside of the study should be captured.

Symptoms reporting for ILI will be conducted between Day 1 through Day 361 (Month 12)/EoS as described in [Section 8.9.4](#).

All RT-PCR-confirmed influenza ([Section 8.11.5](#)) and RT-PCR-confirmed symptomatic COVID-19 infections will be recorded as MAAEs along with relevant concomitant medications, hospitalizations, outpatient medical care, and details about severity, seriousness, and outcome. Asymptomatic RT-PCR-confirmed COVID-19 infections are not to be recorded as MAAEs.

8.9.3 Safety Telephone Calls

A safety telephone call is a telephone call made to the participant by trained site personnel. This call will follow a script, which will facilitate the collection of relevant safety information. Safety telephone calls will follow a schedule for each participant, as shown in the SoE (Table 1). The participant will be interviewed according to the script about occurrence of AEs, MAAEs, SAEs, AESIs, AEs leading to withdrawal from study participation, concomitant medications associated with those events, and any non-study vaccinations (Section 8.11.14). All safety information collected from the telephone contact must be documented in source documents as described by the participant and not documented on the script used for the safety telephone contact. An unscheduled follow-up safety call may be triggered if an eDiary record results in identification of a relevant safety event.

